5.5.2 Sponsor Follow-Up

For serious adverse events, adverse events of special interest, and pregnancies, the Sponsor or a designee may follow up by telephone, fax, electronic mail, and/or a monitoring visit to obtain additional case details and outcome information (e.g., from hospital discharge summaries, consultant reports, autopsy reports) in order to perform an independent medical assessment of the reported case.

5.6 ADVERSE EVENTS THAT OCCUR AFTER THE ADVERSE EVENT REPORTING PERIOD

The sponsor should be notified if the investigator becomes aware of any serious adverse event or adverse event of special interest that occurs after the end of the adverse event reporting period (defined as 30 days after the last dose of study drug or until initiation of new anti-cancer therapy, whichever occurs first, for adverse events and until 90 days after the last dose of study drug or until initiation of new anti-cancer therapy, whichever occurs first for serious adverse events and adverse events of special interest), if the event is believed to be related to prior study drug treatment. All such events should be reported until the end of study (defined as the date after which all enrolled patients who remain alive have been followed for at least 18 months from the start of study drug.)

The investigator should report these events directly to Roche or its designee, either by faxing or by scanning and e-mailing the Serious Adverse Event/Adverse Event of Special Interest Reporting Form with use of the fax number or e-mail address provided to investigators.

5.7 EXPEDITED REPORTING TO HEALTH AUTHORITIES, INVESTIGATORS, INSTITUTIONAL REVIEW BOARDS, AND ETHICS COMMITTEES

The Sponsor will promptly evaluate all serious adverse events and adverse events of special interest against cumulative product experience to identify and expeditiously communicate possible new safety findings to investigators, IRBs, ECs, and applicable health authorities based on applicable legislation.

To determine reporting requirements for single adverse event cases, the Sponsor will assess the expectedness of these events with the use of the following reference document:

- Atezolizumab Investigator's Brochure

The Sponsor will compare the severity of each event and the cumulative event frequency reported for the study with the severity and frequency reported in the applicable reference document.

Reporting requirements will also be based on the investigator's assessment of causality and seriousness, with allowance for upgrading by the Sponsor as needed.

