3.1 DESCRIPTION OF THE STUDY

This is a Phase II, open-label, prospective, multicenter study designed to evaluate the efficacy and safety of single-agent atezolizumab as a first-line therapy in patients with locally advanced or metastatic NSCLC. In addition, the primary biomarker objective is to measure bTMB and evaluate whether it can predict for improved clinical outcome with atezolizumab.

There will be approximately 150 patients with Stage IIIB–IVB, locally advanced or metastatic, EGFR/ALK–negative NSCLC who are immunotherapy-naive enrolled at approximately 25–30 study sites in the United States.

Figure 1 illustrates the study design.

Figure 1 Study Schema

AJCC = American Joint Committee on Cancer; Dx = diagnosis; ECOG = Eastern Cooperative Oncology Group; EGFR/ALK = epidermal growth factor receptor/anaplastic lymphoma kinase; IASLC = International Association for the Study of Lung Cancer; IV = intravenous; mets = metastases; NSCLC = non-small cell lung cancer; PD = progressive disease; PS = performance status; q3w = once every three weeks; RECIST = Response Evaluation Criteria in Solid Tumors.

^a Staging criteria based on the IASLC Lung Cancer Staging Project proposed for the eighth edition of the AJCC NSCLC staging system (see [Appendix 3](#)). Patients with histologically or cytologically confirmed Stage IIIB-IV NSCLC based on the seventh edition of the AJCC NSCLC staging system are also eligible for study entry.

^b Blood samples will be taken at baseline and at progression (all samples will be tested retrospectively).

^c Treatment beyond RECIST v1.1 progression may be permitted if the patient continues to derive clinical benefit as determined by the investigator.

Atezolizumab (fixed dose of 1200 mg) will be administered intravenously on Day 1 of each 21-day cycle.

Patients who meet the Response Evaluation Criteria in Solid Tumors (RECIST) v1.1 criteria for progressive disease (PD) at any timepoint during treatment will be permitted to continue atezolizumab treatment if there is evidence of clinical benefit, defined as meeting all of the following criteria:

- Evidence of clinical benefit as assessed by the investigator
- Absence of symptoms and signs (including worsening of laboratory values [e.g., new or worsening hypercalcemia]) indicating unequivocal progression of disease
- No decline in ECOG performance status that can be attributed to disease progression

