3.2 END OF STUDY AND LENGTH OF STUDY

The end of this study is defined as the date after which all enrolled patients who remain alive have been followed for at least 18 months from study-drug initiation. Thereafter, patients *who discontinue study drug* will be followed for *optional* long-term survival as described in Section [4.5.8](#).

Patients who remain on study drug will continue therapy until they have received a total of 2 years of atezolizumab treatment (32 cycles), and will be followed for safety. Survival data will be collected during the optional long-term follow up period every 3-months for the first year, then every 6 months thereafter, for up to 5 years from enrollment of the first patient into the study, until the last patient dies, withdraws consent, or is lost to follow-up, whichever occurs first

The total length of the study, from screening of the first patient to the end of the study, is expected to be approximately 3 years. *In addition, the Sponsor may decide to terminate the study at any time.*

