5.3.1 Adverse Event Reporting Period

Investigators will seek information on adverse events at each patient contact. All adverse events, whether reported by the patient or noted by study personnel, will be recorded in the patient's medical record and on the Adverse Event eCRF.

After informed consent has been obtained **but prior to initiation of study drug**, only serious adverse events caused by a protocol-mandated intervention (e.g., invasive procedures such as biopsies, discontinuation of medications) should be reported (see Section 5.4.2 for instructions for reporting serious adverse events).

After initiation of study drug, all adverse events will be reported until 30 days after the last dose of study drug or until initiation of new anti-cancer therapy, whichever occurs first, and serious adverse events and adverse events of special interest will continue to be reported until 90 days after the last dose of study drug or until initiation of new anti-cancer therapy, whichever occurs first.

For patients participating in the optional long term follow-up (as outlined in Section 4.5.9) who continue to receive atezolizumab, all AE's will be reported until 30 days after the last dose of atezolizumab during this period of the study. Additionally, serious adverse events and non-serious adverse events of special interest will be reported until 90 days after the last dose of atezolizumab.

Female patients of childbearing potential will be instructed to immediately inform the investigator if they become pregnant during the optional long-term follow-up period or within 5 months after receiving their last dose of atezolizumab.

Pregnancies are to be reported to the Sponsor, as applicable, according to the same guidelines as outlined in Section 5.4.3.1.

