5.3.5.8 Deaths

For this protocol, mortality is an efficacy endpoint. Deaths that occur during the protocol-specified adverse event reporting period (see Section 5.3.1) that are attributed by the investigator solely to progression of NSCLC should be recorded on the Study Completion/Study Discontinuation eCRF. All other on-study deaths, regardless of relationship to study drug, must be recorded on the Adverse Event eCRF and immediately reported to the Sponsor (see Section 5.4.2).

Death should be considered an outcome and not a distinct event. The event or condition that caused or contributed to the fatal outcome should be recorded as the single medical concept on the Adverse Event eCRF. Generally, only one such event should be reported. If the cause of death is unknown and cannot be ascertained at the time of reporting, "**unexplained death**" should be recorded on the Adverse Event eCRF. If the cause of death later becomes available (e.g., after autopsy), "unexplained death" should be replaced by the established cause of death. The term "sudden death" should not be

used unless combined with the presumed cause of death (e.g., "sudden cardiac death"). Deaths that occur after the adverse event reporting period should be reported as described in Section 5.6.

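### Section 5.6 was not updated when dosing was extended past the end of study, so for some patients its late-event reporting window closes before it opens

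*Protocol*

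**What the plan says.** **Late events.** Protocol Section 5.6 asks the investigator to notify the sponsor of an SAE or AESI that comes to light after the reporting period, "if the event is believed to be related to prior study drug treatment". It sets a stop: "All such events should be reported until the end of study", defined there as "the date after which all enrolled patients who remain alive have been followed for at least 18 months from the start of study drug".

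**Sections that rely on 5.6.** Section 5.4.2.2 refers SAEs more than 90 days after the last dose to 5.6. Section 5.3.5.8 does the same for deaths: "Deaths that occur after the adverse event reporting period should be reported as described in Section 5.6". Section 5.6 itself does not name deaths.

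**Dosing.** Section 3.2: "Patients who remain on study drug will continue therapy until they have received a total of 2 years of atezolizumab treatment (32 cycles". Section 3.1 and Appendix 1b repeat this.

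**Ordinary reporting period.** Section 5.3.1 ties reporting to the last dose: "After initiation of study drug, all adverse events will be reported until 30 days after the last dose of study drug", and 90 days for SAEs and AESIs, in each case ending earlier if new anti-cancer therapy starts. For patients still receiving drug in optional long-term follow-up it adds that "serious adverse events and non-serious adverse events of special interest will be reported until 90 days after the last dose of atezolizumab".

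**Other statements on late events.** Appendix 1a footnote x asks for late SAEs and AESIs with no end date and no relatedness condition. SAP Section 4.6.2 stops such reporting at study completion. Appendix 1b marks adverse events during dosing, at treatment completion and at the 30-day call; the later survival calls collect survival information only.

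**The concern.** Section 5.3.1 has a clause for patients dosed during long-term follow-up. Section 5.6, which takes over where 5.3.1 ends, has none. Its closing date is fixed for the whole trial, while its opening date moves with each patient's last dose. Once dosing may run past the closing date, the two can cross.

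Whether a related serious event arising after day 90 is reportable then depends on when a patient enrolled and how long treatment lasted. A patient who stopped early has a 5.6 window that may last months or years. A patient enrolled late who completes treatment, and so is among the most exposed in the trial, has none. Section 6 of the protocol promises safety reporting for patients who remain on drug. For them that report would have no 5.6 duty behind it after day 90. ORR and the biomarker analyses are not affected.

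**Working it through.** The plan states no figure for this point, so there is nothing to reproduce. The check is date arithmetic, with 1 month = 30.4375 days.

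**Inputs**
- End of study: 18 months after the last patient's first dose (Protocol 3.2, 5.6).
- Cycle length 21 days: drug "will be administered intravenously on Day 1 of each 21-day cycle" (Protocol 3.1). Maximum 32 cycles (3.2).
- Ordinary SAE/AESI period: last dose + 90 days (5.3.1, 5.4.2.2).
- Accrual: 12 months (assumption in SAP 4.1), or about 18 months, from a total length of about 3 years (3.2): 36 − 18 = 18. Even accrual is my assumption.

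**Step 1. Last-enrolled patient, on schedule**
- End of study: 18 × 30.4375 = day 548.
- Dose 32: 31 × 21 = day 651, which is 103 days (3.4 months) after end of study.
- 90-day period closes: 651 + 90 = day 741, which is 193 days (6.3 months) after end of study.

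Section 5.6 would open on day 741 but closed on day 548.

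**Step 2. Contrast: first-enrolled patient, 12-month accrual, same 32 doses**
- End of study: 30 × 30.4375 = day 913.
- 5.6 window: 913 − 741 = 172 days (5.7 months).

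The same exposure gives 172 days of late reporting in one case and none in the other.

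**Step 3. Who can be affected.** A patient who starts x months before the last one reaches end of study at 18 + x months from his or her own first dose. Dosing can pass that date if x < 3.4. The 90-day period of a 32-cycle completer passes it if x < 6.3. Enrolments = months ÷ accrual × 150, using unrounded months (3.39 and 6.34):

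| Group | 12-month accrual | 18-month accrual |
|---|---|---|
| Could be dosed past end of study (last 3.4 months) | 42 | 28 |
| No 5.6 window if 32 cycles completed (last 6.3 months) | 79 | 53 |

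These are enrolments, not affected patients. They must be multiplied by the fraction still on drug, which the documents do not give. At an assumed 10–20%, the first row becomes about 3–8 patients and the second about 5–16.

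**Step 4. Sensitivity.** Thirty-two 21-day cycles last 672 days (22.1 months), not 2 years. If the limit is read as 24 calendar months, the first row becomes 6.0 months (75 or 50 enrolments) and the second 9.0 months (112 or 75). The protocol should reconcile the two expressions. The finding holds under either.

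**Step 5. Other patients.** Anyone whose last dose falls in the 90 days before end of study also has no 5.6 window, whatever the number of cycles, unless new anti-cancer therapy starts before end of study and so ends the ordinary period early.

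**The case against.** The strongest reply is that these patients are not left without safety reporting. Section 5.3.1 requires all adverse events to 30 days, and SAEs and AESIs to 90 days, after the last dose in long-term follow-up. The general clauses of 5.3.1 and 5.4.2.2 have no end-of-study cap. Section 3.2 says patients remaining on drug are followed for safety, and Appendix 1b collects adverse events throughout dosing. All of this stands. A reader might infer from 5.6 that reporting stops before the last dose; the documents do not support that. The gap begins after day 90.

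A reader might also infer that a drug-related death in long-term follow-up would be recorded only as survival status. Inside the ordinary reporting period this is wrong: Section 5.3.5.8 requires any on-study death not due solely to NSCLC progression to be recorded as an adverse event and reported immediately. It can be true only afterwards.

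Appendix 1a footnote x could be said to fill the gap, since it has no end date. It does not settle the matter. It conflicts with 5.6 on both end date and relatedness, and footnote e of the same appendix refers long-term follow-up to Appendix 1b, whose survival calls carry no adverse-event mark. The documents disagree here; they are not silent.

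Lastly, 5.6 is a passive duty, the patients are few, and harm requires a related serious event more than 90 days after the last dose that reaches the investigator. The documents give no rate for that, and I estimate none. This limits the size of the point but does not make the rule work.

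**Conclusion.** The point holds as a defect in the end date of Section 5.6. For patients dosed past the end of study, or last dosed in the 90 days before it, the late-reporting duty expires before it can begin, and Sections 5.4.2.2 and 5.3.5.8 refer their late events to a rule that cannot apply. The last-enrolled patient on schedule passes out of the 90-day period 193 days after 5.6 has closed.

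The two groups should be kept apart. About 28–42 of 150 enrolments start late enough to be dosed past the end of study. The larger figure of 53–79 counts those who would have no 5.6 window if they completed 32 cycles, and should not be read as the number dosed past that date. Both rest on even accrual over 12 or 18 months and dosing exactly every 21 days, and both come before multiplying by the fraction still on drug. The likely number of patients is small. The change is still worth making, because it concerns individual drug-related serious events.

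**What to change.** In Section 5.6, add that for patients whose 90-day period ends after the end of study, including those dosed in optional long-term follow-up, the existing duty to notify the sponsor of related SAEs, AESIs and deaths that the investigator learns of continues to the end of their long-term follow-up. State what applies to a patient in this group who does not consent to that follow-up.

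With follow-up capped at 5 years from first enrolment, this restores a usable window. For the last-enrolled completer on schedule it is up to 60 − (12 + 24.3) = 23.7 months with 12-month accrual, or 60 − (18 + 24.3) = 17.7 months with 18-month accrual.

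Then align three places with it: Appendix 1a footnote x (end date and relatedness), SAP Section 4.6.2 (stop at study completion), and the cross-reference in Section 5.3.5.8, by naming deaths in 5.6.

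The cost is one sentence in 5.6, these alignments, and a small added reporting load for a few patients. Active event collection at every survival call is not needed. Section 4.5.9 has the sponsor's designee manage that data collection, so investigator causality judgements there would be a larger change.

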6. STATISTICAL CONSIDERATIONS AND ANALYSIS PLAN

There will be approximately 150 patients enrolled in the study. Safety analyses will include all patients who receive at least one dose of study drug. Biomarker analyses will include all patients who received at least one dose of study drug and have baseline biomarker assessment. The primary efficacy analysis measured by ORR and the primary biomarker analysis will be performed after all patients complete 6 months of follow-up (i.e., 6 months after the final patient has been enrolled). The final analysis will be performed at the end of the study, 18 months after all patients have been enrolled. *The overall survival analysis will be updated once the long-term follow-up data is available, and will be summarized in a separate report. Safety reporting for patients who remain on study drug will also be included.*

In addition, OS data collected through the external death registry data after study completion during the optional long-term follow-up will be updated periodically (e.g., every 1–2 years) based on data availability.

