4.5.9 Optional Long-Term Follow-Up

Patients enrolled in the study will be asked to participate in optional long-term follow-up, which will include collection of long-term survival data beyond the end of the study. This long-term data collection will be managed by the Sponsor's designee. The patient may withdraw consent from optional long-term follow-up at any time during or after the study by e-mail.

Long-term follow-up will be initiated after the study end or if the study is terminated for any reason. *Survival data will be collected during the optional long-term follow-up period every 3 months for the first year, then every 6 months thereafter for up to 5 years from enrollment of the first patient into the study, until the last patient dies, withdraws consent, or is lost to follow-up, whichever occurs first.*

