6.4.2 Secondary Efficacy Endpoints

Secondary efficacy endpoints include OS and investigator (INV)-assessed duration of response (DOR) and PFS per RECIST v1.1.

DOR will be analyzed for the subset of patients who achieved an objective response. DOR is defined as the time from the initial occurrence of documented CR or PR until documented disease progression as determined by the investigator, or death, whichever occurs first. Median and range will be presented for a descriptive summary.

PFS is defined as the time from the first dose of study drug to the time of disease progression or death from any cause during the study, whichever occurs first. Patients who have not experienced disease progression or death at the time of analysis will be censored at the time of the last tumor assessment. Patients with no post-baseline tumor assessment will be censored at the time of first dose.

OS is defined as the time from the first dose of study drug to the time of death from any cause during the study. Patients who are still alive at the time of analysis will be censored at the time of their last study assessment (for active patients) or at the last date known alive (for patients in follow-up).

PFS and OS of patients in this study will be summarized graphically and with descriptive statistics such as median and landmark PFS by using the Kaplan-Meier (K-M) methodology. The Brookmeyer-Crowley methodology will be used to construct the 95% CI for the median PFS and OS (Brookmeyer and Crowley 1982). K-M methods will also be used to estimate landmark PFS, along with the corresponding 95% CI, by using Greenwood's formula.

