Appendix 1b
Optional Long-Term Follow-Up Schedule of Assessments

Activity	All Treatment Cycles	Treatment Completion/DC b,c	Safety Follow-Up (Phone Call)	Overall Survival Follow-Up (Phone Call)	Study Completion/DC
	Continued dosing Every 21 (±3) Days ^a		30 days post-last treatment	Every 3 months for the first year, then every 6 months thereafter, or up to 5 years from enrollment of the first patient into the study until the last patient dies, withdraws consent, is lost to follow-up, whichever occurs first	
Study drug administration	x				
Adverse Event	x	x	x		
Survival Information				x	x

DC=discontinuation
 
^a Patients on study drug will continue therapy until they have received a total of 2 years of atezolizumab treatment (32 cycles).
 
^b Patients will be asked to return to the clinic no more than 30 days after the last dose for a treatment discontinuation visit. Note that the Study Discontinuation eCRF should not be completed until after the patient has discontinued from the study.
 
^c Patients who complete the optional long-term follow-up study will return to the clinic for a study completion visit within 30 days following study completion. Patients who discontinue the study prematurely will return to the clinic for a study discontinuation visit within 30 days following discontinuation from the study.
					

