All patients will undergo tumor assessment at baseline and every 6 weeks (\pm 7 days) thereafter regardless of dose delays for the first 12 months following Cycle 1, Day 1. After 12 months, tumor assessment will be required every 9 weeks (\pm 7 days); tumor assessments will continue until disease progression per RECIST v1.1 or loss of clinical benefit, consent withdrawal, study discontinuation, study completion or death, whichever occurs first. All patients will be followed for survival and anti-cancer therapy while in the study and will be given the option of participating in a long-term follow-up during which survival data will be collected from public resources (e.g., death dates from online obituaries or the National Death Index).

Safety will be assessed on the basis of vital sign measurements, ECOG performance status scores, physical examination findings, clinical laboratory test results, and the frequency, severity, and relationship to atezolizumab of adverse events.

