4.5.2 Secondary Efficacy Endpoints

Secondary efficacy endpoints include disease control rate (DCR), duration of response (DOR), and PFS, per RECIST v1.1, and OS. Disease control rate (DCR) is defined as the rate of patients with complete or partial response as best response or stable disease maintained for 24 weeks per RECIST v1.1. DOR will be analyzed for the subset of patients who achieved an objective response. DOR is defined as the time from the initial occurrence of documented CR or PR until documented disease progression as determined by the investigator or death, whichever occurs first. Median and range will be presented for a descriptive summary. Responders with no PD or death, DOR will be censored at last post-baseline tumor assessment. Responders with no post-baseline tumor assessment will be censored at the date of first dose plus 1.

PFS is defined as the time from the first dose of study drug to the time of disease progression or death from any cause during the study, whichever occurs first. Patients who have not experienced disease progression or death at the time of analysis will be censored at the time of the last tumor assessment. Patients with no post-baseline tumor assessment will be censored at the date of first dose plus 1.

OS is defined as the time from the first dose of study drug to the time of death from any cause during the study. Patients who are still alive at the time of analysis will be censored at the date of their last study assessment (for active patients) or at the last date known alive (for patients in follow-up). Patients with no post-baseline assessment will be censored at the date time of first dose plus 1.

PFS and OS of patients in this study will be summarized graphically and with descriptive statistics such as median and landmark PFS by using the Kaplan-Meier (K-M) methodology. The Brookmeyer-Crowley methodology will be used to construct the 95% CI for the median PFS and OS (Brookmeyer and Crowley 1982). K-M methods will also be used to estimate landmark PFS and OS at various time points (i.e., 6, 12, 18, and 24 months), along with the corresponding 95% CI, by using Greenwood's formula.

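### Long-term OS draws on two sources, scheduled phone contact and a death registry, with no rule for patients the registry does not match; the tail of the updated curve is biased downward for those the calls miss

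*Protocol*

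**What the plan says.** The current text describes long-term survival collection in three ways.

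- **Scheduled contact.** Protocol 4.5.9: "Survival data will be collected during the optional long-term follow-up period every 3 months for the first year, then every 6 months thereafter". The schedule stops no later than 5 years after the first patient was enrolled. Appendix 1b has a column for "Overall Survival Follow-Up", marked as a phone call. Participation needs additional consent (Protocol 3.1).
- **Registry as an addition.** Protocol Section 6 first says: "The overall survival analysis will be updated once the long-term follow-up data is available, and will be summarized in a separate report". It then adds that "OS data collected through the external death registry data after study completion during the optional long-term follow-up will be updated periodically", for example every 1–2 years.
- **Public sources only.** SAP Section 3: "survival data will be collected from public resources (e.g., death dates from online obituaries or the National Death Index"). The SAP mentions no phone contact.

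The OS rules are nearly the same in both documents. Protocol 6.4.2: "OS is defined as the time from the first dose of study drug to the time of death from any cause during the study". Living patients who are active are censored at their last study assessment; the others "or at the last date known alive (for patients in follow-up"). SAP 4.5.2 likewise censors "at the last date known alive (for patients in follow-up"). Neither document gives a registry completeness date or a rule for a patient with no match.

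**The concern.** A registry search returns dates of death. If a patient last contacted at the end of study is later found dead, the death enters at its true, late time. If that patient is alive, and a non-match is not treated as evidence of life, the patient leaves the risk set at the last contact. Time at risk after last contact is then credited only to patients who went on to die. Censoring depends on the outcome, and the Kaplan-Meier curve falls too fast.

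OS is a secondary endpoint, and Section 6 commits the sponsor to an updated OS report. The late part of the curve is what the long-term follow-up adds, and it is the part exposed to this bias.

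**Working it through.** The plan states no long-term OS figure, so there is none to reproduce. The size was derived under stated assumptions.

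**Inputs.** Accrual of 12 months and follow-up of 18 months after the last patient (SAP 4.1), so end-of-study contact falls c months after first dose, with c taken as uniform on 18 to 30. Assumed: exponential OS with median m, so λ = ln 2 / m; registry searched L = 24 months after end of study; a fraction q of patients not reached by phone after end of study. Reached patients are treated as known alive up to the search.

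**Formula.** Among patients alive at t (t ≤ 18 + L), those past their end-of-study contact who survive to the search are missing from the risk set. Their share, if nobody is phoned, is

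D(t) = (1/12) ∫ exp(−λ(c + L − t)) dc, for c from 18 to min(t, 30).

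The apparent hazard is λ / (1 − q·D(t)), and apparent OS is exp(−its integral from 0 to t).

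**Registry only (q = 1), at 36 months.**
- m = 14, λ = 0.0495: D = (e^(−6λ) − e^(−18λ)) / (12λ) = (0.743 − 0.410) / 0.594 = 0.56. The hazard is inflated by 1/(1 − 0.56) = 2.3.
- m = 20, λ = 0.0347: D = (0.812 − 0.536) / 0.416 = 0.66. The hazard is inflated about threefold.

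| OS at month | m = 14: true | registry only | m = 20: true | registry only |
|---|---|---|---|---|
| 18 | 41.0% | 41.0% | 53.6% | 53.6% |
| 24 | 30.5% | 29.6% | 43.5% | 42.3% |
| 36 | 16.8% | 10.9% | 28.7% | 17.7% |
| 42 | 12.5% | 4.5% | 23.3% | 7.8% |

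Simulation under the same assumptions agrees to within a few tenths of a point.

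**Partial phone contact, 36-month OS.** Half reached (q = 0.5): 14.3% and 24.6%. Four in five reached (q = 0.2): 15.9% and 27.3%, that is 0.9 and 1.4 points low. All reached (q = 0): no bias in this formula.

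**Simulation with the medians in Protocol 3.3.2** (12.5 and 22.6 months; 150 patients, 2,000 replicates, end of study at month 30). Data cut at month 60 from first enrolment:

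| Rule | 36-month OS, m = 12.5 / 22.6 | 48-month OS, m = 12.5 / 22.6 |
|---|---|---|
| True | 13.6% / 33.1% | 7.0% / 22.9% |
| Registry only, survivors frozen at end of study | 10.5% / 23.8% | 2.4% / 6.4% |
| All phoned, last call 0–6 months before cut | 13.6% / 33.3% | 6.8% / 22.8% |
| 20% not phoned, their registry deaths counted | 13.0% / 32.0% | 6.1% / 20.6% |
| 20% not phoned, no registry | 13.6% / 33.3% | 6.9% / 22.8% |
| Registry, unmatched censored at the cut | 13.6% / 33.3% | 7.0% / 23.1% |

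An earlier search is worse. With a cut at month 42, one year after end of study, registry-only 36-month OS is 2.4% and 6.0%. Even with everyone phoned it is 11.3% and 29.9%, because deaths run to the cut while survivors stop at their last call. That run assumed a lag of up to 6 months; calls are 3-monthly in the first year, so it overstates the effect.

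**Planned landmarks.** The SAP lists 6, 12, 18 and 24 months. Registry-only 24-month OS is 24.9% against 26.4% and 45.9% against 47.9% at the month-42 cut, and 25.9% and 46.9% at month 60. Median OS moves by less than 1 month.

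**The case against.** The strongest objection is that the current protocol does not rely on a registry alone. Calls every 3, then 6, months renew the last date known alive. Section 6 brings in the registry as an addition, and its natural reading is that both sources cover the same consenting patients. Patients still on drug are seen every 21 days. A reader might infer from the registry text that every survivor is frozen at the end of study and late OS is badly wrong. The documents do not support that: only the SAP, read alone, describes such a design.

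A second objection is that OS is defined as death during the study, while long-term follow-up starts after it. Read literally, later registry deaths are not events, and the update report has no written censoring rule at all. This does not remove the problem. On the literal reading the promised update could contain no new deaths. If the deaths are counted, the only censoring rule on paper for patients in follow-up is the one that produces the bias.

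Third, the documents do not say that a non-match leaves the alive date unchanged; that is an inference from their silence. Treating a non-match as alive to the registry's completeness date would remove the bias, but nothing in the text says to do so.

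Fourth, the planned landmarks barely move. This stands. Survivors are followed for at least 18 months, so 18-month OS is unaffected, and a 24-month shift of 1 to 2 points compares with a standard error of about 4 points: √(0.435 × 0.565 / 150) = 0.040.

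**Conclusion.** The sources of long-term survival data conflict across Protocol Section 6, Protocol 4.5.9 with Appendix 1b, and SAP Section 3. Under the written censoring rule, counting registry deaths in patients the calls do not reach biases the tail of the updated OS curve downward.

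The size depends on how many are reached. With a registry alone, 36-month OS is about 6 points low for a median of 14 months and 11 points low for a median of 20. With 80% reached it is about 1 to 1.5 points low. With all reached it is near zero away from the data cut. These figures assume exponential OS, 12-month uniform accrual and a search 24 months after end of study; the medians of 14 and 20 months and the fractions reached are also assumptions.

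It would be wrong to infer that the SAP's 18- and 24-month estimates are compromised: the first is unaffected and the second shifts by at most about 2 points. OS is a secondary endpoint summarised descriptively in a study the protocol calls hypothesis-generating. The plan should be corrected, but this does not threaten its primary conclusions.

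**What to change.** Choose one of two options.

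1. **Phone contact only.** Delete the registry paragraph in Protocol Section 6 and the public-resources clause in SAP Section 3, so that the contact in Protocol 4.5.9 and Appendix 1b is the only source.
2. **Keep a registry.** Restrict it to a source with a known completeness date, which excludes obituaries, and add to Protocol 6.4.2 and SAP 4.5.2: *In the long-term OS update, one common cutoff applies to deaths and survivors: a searched patient not found dead is censored at the registry completeness date, and registry deaths after that date are not counted.*

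In either case, extend the OS definition for the update report beyond deaths during the study, so that deaths in long-term follow-up count.

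The cost is wording only. Option 1 loses deaths in patients not reached by phone and assumes that being unreached is unrelated to prognosis. Option 2 assumes that deaths are matched completely up to the completeness date; missed deaths would bias OS upward.
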